Specific Aim 1: To examine whether BreESTim could have better analgesic effects on PLP

It is hypothesized that BreESTim has better analgesic effect than EStim, and the analgesic effect is accompanied by elevated electrical pain thresholds. Patients with PLP will receive both BreESTim and EStim in a randomized order with at least 3 days apart. The same amount of stimulation (120 electrical stimuli) at comparable intensities will be used as in our recent studies. According to our preliminary data, we expect that BreESTim has greater pain reduction and longer lasting effect. These results will parallel with increased electrical pain thresholds after BreStim, i.e., desensitization, as compared with EStim.

Specific Aim 2: To examine whether BreESTim-induced analgesic effect is dose-dependent

Similar to taking pain medications, it is hypothesized that there is a dose-response analgesic effect of BreESTim, i.e., an increased "dose" of BreESTim will have a greater impact on reduction of phantom limb pain. Two doses of BreESTim intervention (120 vs. 240 electrical stimuli) will be given to the same amputee with one week apart in a randomized order. According to our preliminary data from 3 subjects, we expect that that a high-dose BreESTim will produce a longer-lasting, but similar degree of pain reduction as compared to a low-dose BreESTim. The findings also suggest a possible cumulative effect of BreESTim, thus leading to a long term effect.

Specific Aim 3: to examine the long-term effect of BreESTim on neuropathic PLP

It is critical to know whether patients will tolerate electrical stimulation and the induced analgesic effect will diminish or the effect will accumulate if patients receive BreESTim repetitively over time, before it is translated into a therapeutic device. It is hypothesized that the BreESTim treatment will produce a greater analgesic effect than the convention electrical stimulation (EStim) treatment in patients after traumatic amputation over a course of 2 weeks (10 consecutive workdays). We will examine the hypothesis by comparing electrical pain threshold and effectiveness in pain reduction between BreESTim and EStim in patients after traumatic amputation of one limb. The analgesic effect will be assessed by pain reduction in visual analog scale and quantitative measurement of electrical sensation and pain thresholds. The effect on general well-being and change in pain medication will be assessed.

4. Research design and methods:

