Power analysis and estimate of sample size for Experiment 1 [name] (our biostatistician consultant) has performed power analysis based on our pilot study and historical data from the literature. A two-way repeated measures ANOVA was used to determine whether any change in VAS score was due to the interaction between INTERVENTION and TIME (i.e. whether one of two interventions is more effective at reducing VAS scores). A power analysis using the G*power computer program (Faul et al. 2007) indicated that a sample of 12 people would be needed to detect a large effect size (> 0.8) with 85% power using a repeated measures two-way ANOVA with alpha at .05, a sample of 14 people would be needed for 90% power. To account for possible subject withdrawal (10%), we plan to recruit 16 subjects. Also to reduce the experimental bias and the order effect, the order of the interventions will be randomized.

Pilot data and sample size for Experiment 2 (Aim 2)

In Experiment 2, the same BreESTim protocol will be used, but at two different doses (120 stimuli vs. 240 stimuli). We have tested the protocol in 4 patients with phantom limb pain after BKA (Figure 5). On average, BreESTim120 and BreESTim240 had similar analgesic effects. VAS decreased from 6.4 to 3.5 after BreESTim120, and from 5.9 to 3.5 after BreESTim300. However, the analgesic effect lasted longer after BreESTim240 (26.1 hours) than after BreESTim120 (14.5 hours). Similar to Experiment 1, these data are from IRB approved study MS-20-1032

analgesic effects were paralleled with similar degrees of change in EPT without changes in other thresholds.

[figure not shown]

[figure not shown]
Figure 5 BreESTim has a dose-response effect on the duration, not the degree of analgesic effects on phantom limb pain.

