It is expected that electrical pain threshold will be further increased after BreESTim with parallel reduction in pain perception, while there is no or minimum change after EStim and no significant change in pain perception. Pain threshold will be measured using QST. Pain perception will be characterized by duration and amount of change in pain on visual analog scale (VAS), i.e., how much pain is reduced and how long it lasts. As such the effect of treatment is quantified by reduction x hours.

The secondary outcome measurement will be General Well-Being (GWB) Schedule Survey and Center for Epidemiologic Studies Depression Scale (CES-D), NIMH Survey to examine the possible effect of pain reduction on general well-being, depression and quality of life of the patients. These surveys have been well validated and commonly used (Sherman et al. 1984; Wartan et al. 1997; Kooijman et al. 2000).

The long-term BreESTim treatment is expected to have some cumulative analgesic effects. However, we decide to keep the same regime of medications, because change in medications will be a confounding factor. Therefore, the subjects will be explicitly instructed to maintain the same dose and frequency of pain medications after the BreESTim treatment even if pain is improved. The collaborating investigator [name] will screen and monitor their medications. This is exploratory at this time. If the baseline pain level improves after the 2-week BreESTim treatment, a clinical trial is warranted. Change in pain medications may be explored further in the future studies.

- **Experimental setup (BreESTim and EStim protocols and measurement)**

Experiment 1 We plan to use our recent BreESTim and EStim protocols (Li et al. 2013; Li et al. 2014). Briefly, subjects will be seated comfortably with the arm on the experimental table (Fig 8). Subjects will wear a facemask that will be connected to a Pneumotach system to record breathing signals and to prevent hyperventilation. Surface electrodes will be trimmed to be applied to the median nerve ipsilateral to the affected side proximal to the wrist line (see Fig 8). Note that important acupuncture points (Neiguang and Waiguan) are located beneath the electrodes. So these points will be stimulated during both BreESTim and EStim).

[figure not shown]

Figure 8 Experimental settings. On the right panel, an electrical stimulus (Lower) is triggered when the airflow rate (Upper) of a forceful inhalation reaches 40% of its maximum value.

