Two interventions (BreESTim vs. EStim) will be given to the same subject on a different day with at least 7 days apart. As in previous studies(Li et al. 2013; Li et al. 2014), a total of 120 electrical stimuli will be delivered for each intervention. The order of interventions will be randomized and balanced across subjects. Both interventions will be given at the same time of the day, as determined by subject's schedule. It is important to emphasize that subjects will be explicitly instructed to maintain the same pain regime even they feel that treatment has helped in pain reduction, such that pain reduction is mainly related to BreESTim or EStim.

Outcome measurement includes visual analogue scale (VAS) and Quantitative Sensory Testing (QST) and Hear rate variability (HRV). The VAS method has been extensively used and validated (McCarthy et al. 2005). Using VAS to rate pain intensity has been considered a standardized measurement to evaluate effectiveness of deep brain stimulation for pain management in a multi-center study by Medtronic (Medtronic, Minneapolis, MN). These results have been reported to US Food and Drug Administration for judgment on the efficacy of pain management(Coffey 2001). In the project, we plan to use a modified VAS to quantify pain reduction. As used in our pilot study (Li et al. 2012a; Li 2013), the effect of pain reduction is characterized by duration and amount of change in pain on VAS, i.e., how much pain is reduced and how long it lasts. As such the effect of treatment is quantified by reduction×hours. The effect and the intensity of stimulation will be recorded daily during the course of treatment. For VAS, the duration of analgesic effect from the intervention will also be recorded. VAS scores will be obtained before and 10 minutes after. Post-intervention VAS will be also assessed through follow-up phone calls every 4 hours except night time (10pm – 7am). It is important to emphasize that subjects will be explicitly instructed to maintain the same pain medication regimen even if they feel that treatment have helped in pain reduction.

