Experiment 2 The aim of this experiment is to explore this “dose-response” effect of BreESTim, by comparing the analgesic effects of two doses of single-session BreESTim. The same BreESTim protocol in Exp 1 will be used for Exp 2. In Exp 2, only BreESTim will be used. Two doses of BreESTim (120 vs. 240 electrical stimuli) will be given at least one week apart in a randomized order. Outcome measures, including VAS, QST thresholds, will be recorded pre- and 10 minutes post-intervention. Duration of analgesic effect (lasting hours) will also be recorded.

Experiment 3 The experimental set-up will be similar to Experiments 1&2. There are two different interventions – BreESTim and EStim. Each intervention consists of 240 stimuli/session (about 40-50 min/session), 1 session/day for 10 sessions (over 2 weeks, no treatment in the weekends). After a follow-up (wash-out) period of two weeks, the same subject will be treated with the other intervention with a same follow-up of 2 weeks. The intensity of stimulation will be increased gradually as patients could tolerate. Aversiveness of electrical stimulation is part of treatment strategy. During EStim, a single-pulse electrical stimulation is delivered to the forearm through surface electrodes randomly, while electrical stimulation is triggered by volitionally effortful inhalation during BreESTim as in Exp 1.

Specimens:

No specimens will be collected

5. Human Subjects

As mentioned above, we plan to recruit a total of 64 amputee subjects with phantom limb pain, including 16 subjects for Aim 1, 18 subjects for Aim 2, and 30 subjects for Aim 3. The number of subjects was estimated based on the pilot data.

• Subject recruitment/assignment

The collaborating physician (Co-I, [name]) will screen patients from the outpatient clinic of TIRR Memorial Hermann Hospital. We plan to register the project on www.clinicaltrials.gov. If patients are not currently seen by [name], but are willing to participate in the project, they need to see [name] for screening and monitoring. In addition, [name] will monitor medical conditions of the patients and manage medical problems as needed. Patients will be recruited and enrolled in the project if they meet the following criteria:

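### In Experiment 3 the next day's session cuts off the daily reduction-times-hours score, the score's baseline is undefined, and the planned ANOVA cannot show whether relief grows or fades over ten sessions

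*Combined protocol and SAP*

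**What the plan says.** Specific Aim 3 (Section 3) sets out to learn whether "the induced analgesic effect will diminish or the effect will accumulate if patients receive BreESTim repetitively over time". Section 4.D, Experimental Design, says that some cumulative effect is expected.

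The Experiment 3 measure is described in the same section: "Pain perception will be characterized by duration and amount of change in pain on visual analog scale (VAS), i.e., how much pain is reduced" and for how long. The treatment effect is the product of the two, VAS reduction times hours.

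Section 4.D, Experimental setup, gives the Experiment 3 schedule as "1 session/day for 10 sessions (over 2 weeks, no treatment in the weekends", with 240 stimuli and about 40 to 50 minutes per session. It describes the set-up as similar to Experiments 1 and 2.

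Under Experiment 1 the same section places VAS readings before and 10 minutes after the intervention, adds follow-up calls every 4 hours outside the night, and states: "The effect and the intensity of stimulation will be recorded daily during the course of treatment". Experiment 1 has one session per intervention, so daily recording over a course fits only Experiment 3.

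The pilot for Experiment 2 (Section 4.C) reports that "the analgesic effect lasted longer after BreESTim240 (26.1 hours) than after BreESTim120 (14.5 hours".

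Section 6 analyses Experiment 3 by a two-way repeated-measures ANOVA. Its factors are intervention and a three-level time factor (pre, post, follow-up), and its variables include both VAS and the modified VAS.

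**The concern.** On the sponsor's own pilot mean, relief from one BreESTim session is still present when the next weekday session begins. This raises three issues.

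- The hours of relief are cut short. EStim relief lasted 2.0 h in the pilot (at 120 stimuli), so the loss falls mainly on BreESTim and narrows the contrast.
- The text available does not say from which VAS the daily reduction is measured in Experiment 3. If it is the VAS just before each session, a patient still better from the day before starts from a lowered baseline, and the score no longer reflects total relief.
- The planned ANOVA has no term for session number. Even with a well-defined score, it does not address change across the ten sessions.

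At stake is the specific question of Aim 3, growth or fading with repetition, more than the overall comparison of the two interventions.

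**Working it through.** **Inputs.** Mean duration after 240 stimuli: 26.1 h (Section 4.C). This is an observed pilot mean with no SD or patient values, so it can be compared with the session gap but not reproduced. On its size, Section 4.C says "We have tested the protocol in 4 patients with phantom limb pain after BKA", while Specific Aim 2 mentions 3 subjects. VAS drop at the higher dose: "from 5.9 to 3.5 after BreESTim300", that is 5.9 − 3.5 = 2.4 points. It is read here, as an assumption, as belonging to the 240-stimuli arm; the label and the patient count need reconciling. Session length: 40 to 50 min. EStim pilot at 120 stimuli: 4.9 to 4.1 (0.8 points) for 2.0 h.

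**Overlap.** End-to-start gap = 24 h − 40 to 50 min = 23.33 to 23.17 h.

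- Overlap = 26.1 − 23.33 = 2.77 h, to 26.1 − 23.17 = 2.93 h. As a share of 26.1 h this is 10.6% to 11.2%.
- Counted start to start: 26.1 − 24 = 2.1 h, or 8.0%.

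**Sessions affected.** Ten sessions have nine gaps. A Monday start gives one weekend gap and eight one-day gaps. A later start gives two weekend gaps and seven one-day gaps. The protocol does not fix the start day, so seven or eight of the ten sessions are affected.

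**Loss in the score at the mean.**

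- Constant relief: 2.4 × 26.1 = 62.6 point-hours uncut. Cut at the next session: 2.4 × 23.33 = 56.0, to 2.4 × 23.17 = 55.6.
- Linear fading to zero at 26.1 h (assumed): the share of area lost is (2.77/26.1)² to (2.93/26.1)² = 1.1% to 1.3%.
- EStim: 0.8 × 2.0 = 1.6. Under constant relief the contrast falls from 62.6 − 1.6 = 61.0 to between 54.4 and 54.0.

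**Share of sessions outlasting the gap.** With normal durations, mean 26.1 h, and an assumed SD of 4 to 16 h, P(duration > 23.2 h) runs from 0.77 down to 0.57.

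**Baseline choice.** Illustration only: start at VAS 5.9, first-session drop 2.4, half of the relief assumed present at the next session, score = immediate reduction × 24 h, five consecutive days.

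| Assumed response to each session | Pre-session baseline, day 1 / 2 / 5 | Fixed pre-course baseline, day 1 / 2 / 5 |
|---|---|---|
| Proportional (2.4/5.9 of current VAS) | 57.6 / 45.9 / 41.1 | 57.6 / 74.7 / 81.7 |
| Constant 2.4-point drop | 57.6 / 57.6 / 57.6 | 57.6 / 86.4 / 111.6 |
| Plateau at 3.5 | 57.6 / 28.8 / 28.8 | 57.6 / 57.6 / 57.6 |

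Day 2, proportional: pre = 5.9 − 1.2 = 4.7; post = 4.7 × (1 − 2.4/5.9) = 2.79; pre-session score (4.7 − 2.79) × 24 = 45.9; fixed score (5.9 − 2.79) × 24 = 74.7 (post unrounded in both products).

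In the first two rows relief accumulates, yet the pre-session score falls or stays flat. In the third, relief is sustained without growing, and the pre-session score halves. The fixed baseline gives the right direction in all three.

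**The case against.** The strongest reply is that the analysis in Section 6 does not use a daily score. In Experiment 3 an intervention is the whole ten-session course, so pre-intervention naturally means before session 1, which is an untreated reference. Raw VAS is analysed beside the modified VAS, the Experiment 3 sample size rests on a difference in VAS, and Section 4.D looks to improvement in baseline pain after the two weeks. A fall in pain over the course would therefore be seen. This stands, and it limits the point. It does not supply a baseline for the modified VAS, and comparing start, end and follow-up says nothing about the path between them.

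The cut-off is also small and its input weak: 2 to 3 h at the mean, less than the 4-hour spacing of the calls, from a handful of patients. This stands too. The loss is nevertheless in one direction and nearly all in one intervention.

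A reader might infer that the protocol resets the baseline every day. It does not say so. The before-and-after reading is written for Experiment 1, and Experiment 3 is called only similar. Figure 7 and some text just before the Experiment 3 power paragraph were not available, and a rule could be there.

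**Conclusion.** The point holds in a limited form. On the protocol's own figures the mean relief from one 240-stimuli BreESTim session outlasts the weekday gap by 2.8 to 2.9 h (2.1 h counted start to start). Daily reduction times hours is thus truncated after seven or eight of ten sessions, mainly for BreESTim. The loss at the mean is up to about 11% with constant relief and about 1% with linear fading. It rests on a mean from 4 patients without an SD.

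The baseline problem is conditional on the pre-session VAS being the reference. A reader might go further and infer that accumulating relief would necessarily look like a diminishing effect. The documents do not support that, because the score can equally stay flat, depending on how each session acts. Nor do they support the inference that a benefit over the course, or the BreESTim versus EStim contrast, would be lost: raw VAS is analysed, and on the pilot figures the contrast stays at about 54 point-hours after the cut-off.

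The firmest part needs no assumption about relief. An ANOVA on pre, post and follow-up with no session term cannot show whether the effect grows or fades over ten sessions, which is what Aim 3 asks.

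**What to change.** Leave the session schedule as it is and amend the measurement and analysis text for Experiment 3.

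- **Reference.** Define every VAS reduction from the VAS before session 1 of that period.
- **Duration.** Use hours of relief, and reduction times hours, only from sessions with no session the next day (the last before a weekend, and session 10). Alternatively, treat the other durations as censored at the start of the next session.
- **Trend.** Add a comparison of the pre-session VAS trend over sessions 1 to 10 between BreESTim and EStim. One suitable form is a mixed model with intervention, session number, their interaction and period, a subject effect, and a term for the session after a weekend. The interaction compares growth or fading between the interventions.

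The cost is wording and one added analysis. If durations are restricted rather than censored, each period yields two usable readings (Monday start) or three, instead of ten. The plan should also state that VAS is taken before every Experiment 3 session. The Experiment 1 text implies this, but it is not written for Experiment 3.

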Power analysis and estimate of sample size for Experiment 3 [name] (our biostatistician consultant) has performed power analysis based on our pilot study and historical data from the literature. Using nQuery Advisor®, we applied the t-test (ANOVA) for difference of VAS in 2 x 2 crossover design with a 0.05 two-sided significance level. To achieve 80% power of detecting a difference in VAS of 3.0 (the difference between the mean of group BreESTim, $\mu_1=4.0$ and the mean of EStim group, $\mu_2=2.0$) assuming that the Crossover ANOVA \sqrt{MSE} is 3.4 (the Standard deviation of differences, σ_d , is 4.8), the sample size is 24. Assuming an expected dropout rate of 20% given the long-term intervention, we proposed to recruit 30 patients in total for Experiment 3.

D. The data collection and measurement techniques are appropriate and effective

- **Experimental Design**

The overall research design is a within-group, randomized controlled study to compare analgesic effects between EStim and BreESTim (single-session in Exp 1, long-term intervention in Exp 3), between BreESTim120 and BreESTim240 (Exp2). We prefer this within-group comparison because 1) pain, by nature, is a subjective perception, it is difficult to control (physical, social, psychological) multi-factors between two groups; 2) It will be fair that all subjects receive the innovative intervention, which is superior to regular electrical stimulation according to our pilot data; 3) according to our recent BreESTim study in patients with spinal cord injury, the duration of analgesic effect was 15 hours after one-session of BreESTim treatment. An interval of one week for washout should be sufficient for Exp 1 & 2. The washout interval will be 2 weeks for Exp 3. It is our experience with subjects with spinal cord injury that an interval of 7 days is sufficient for subjects to return to their baseline after BreESTim treatment. (Li et al. 2016; Karri et al. 2018b; Li et al. 2018) However, we did notice that one subject with post-amputation PLP had carry-over effect for one month(Li et al. 2012a). We plan to screen these patients with long-lasting carry-over effects. These patients will be excluded from the subject should this happen.

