QST includes tactile sensation threshold (TST), electrical sensation threshold (EST), electrical pain threshold (EPT), and thermal thresholds. VAS and QST will be recorded immediately before and 10 minutes after the interventions. In this experiment, we aim to test the central de-sensitization effect of BreESTim. To standardize QST (Li et al. 2015), all thresholds will be measured only on the residual limb at 5 cm above the distal residual limb. The symmetrical site on the contralateral limb will also be localized. After the target areas are localized and marked with a marker, subjects are instructed to stay relaxed in a chair with arms and legs comfortably supported in a symmetrical position. The order of QST will be randomized and balanced across testing sites. The following measurement will be made

Tactile sensation threshold: Tactile sensation threshold will be tested using Von Forey filaments (Touch-Test Sensory Evaluator, North Coast Medical Inc.). The center of the thenar eminence/testing sites on the leg will be marked with a pen symmetrically on both hands. Subjects will be instructed to close their eyes. The experimenter will press the filament at a 90° angle against the marked area until it bows for approximately 1.5 seconds and then removed. Testing will begin with the thinnest 1.65 filament, then progresses to the next monofilaments. An explicit response of touch sensation is defined as tactile sensation threshold.

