Electrical sensation and pain thresholds: The same trimmed electrodes will be used to examine electrical sensation threshold and electrical pain thresholds (electrical stimulator 7SA, Digitimer). A pair of electrodes is placed next to each testing site. For electrical sensation threshold, the intensity of electrical stimulation will start from zero and gradually increase in steps of 0.1 mA. Similarly, subjects will be instructed to close their eyes and to say “yes” when they explicitly feel electrical stimulation. Three repetitions will be made and the average will be used as the electrical sensation threshold. Electrical pain threshold is then measured. The intensity of electrical stimulation will start from the sensation threshold level and increase in steps of 1 mA. The electrical pain threshold is reached when subjects first feel electrical stimulation painful. To improve consistency among subjects, they are advised that the pain threshold level is equivalent to 1 on the 0-10 VAS scale. Similarly, the average of three tests will be used as the electrical pain threshold.

Thermal thresholds: Thermal thresholds (warm sensation, cold sensation, heat pain, cold pain) will be examined using a Medoc PATHWAY system. The established “Limits Full Series” protocol will be selected. Briefly, the protocol contains a series of tests in the following order: 4 tests of cold sensation threshold, 4 tests of warm sensation threshold, 3 tests of cold pain threshold, and 3 tests of heat pain threshold. The 30x30 ATS probe is secured with its center on the testing. Subjects will have an education session prior to the protocol. The averaged value will be used for each threshold.

Heart rate variability as objective outcome measurements: We have been searching for non-invasive objective pain outcome assessment. Heart rate variability has been recognized as a physiological marker for pain assessment (Appelhans and Luecken 2008; Karri et al. 2018b; Karri et al. 2019). We will follow our recent experimental procedures (Karri et al. 2018b; Karri et al. 2019) to collect 5 minutes of Heart Rate recordings before and after the interventions.

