Inclusion criteria: A patient who 1) has neuropathic PLP after amputation of one limb, upper or lower limb; NOTE that BreESTim has been shown to be effective for neuropathic pain management in patients after traumatic and non-traumatic spinal cord injury in recent studies(Li et al. 2016; Li et al. 2018). Therefore, we plan to recruit patients with chronic neuropathic PLP from both traumatic and non-traumatic limb amputation. 2) has chronic pain, >3 months; 3) is between 18 to 75 years of age; 4) is stable on oral pain medications at least two weeks. Patients are instructed to continue their pain medications as prescribed during the intervention period.

Exclusion criteria: Patients will be excluded if they 1) are currently adjusting oral pain medications for their neuropathic pain; 2) have pain, but not neuropathic, e.g., from inflammation at the incision wound of the residual limb; 3) have a pacemaker to avoid possible side effect of electrical stimulation; 4) have amputation in multiple limbs; 5) are not able to follow commands, or to give consent; 6) have asthma or other pulmonary disease; 7) are not medically stable.

Gender will be balanced

Potential subject populations and recruitment: Subjects will be recruited from TIRR outpatient clinic.

6. Data Collection and Analysis

Data collection details have been described above. Data analysis is described here.

Experiment 1 Repeated-measures two-way ANOVA tests with factors INTERVENTION (2 levels, BreESTim and EStim) and TIME (pre- and post-intervention) will be tested on dependent variables, including VAS, QST thresholds (tactile, electrical, and thermal), to determine statistical significance between two interventions. Paired t-tests will be used to compare the duration of lasting hours between two interventions. p value is set at 0.05. As observed in the pilot data, we expect that BreESTim could have central desensitization and analgesic effects on patients with phantom limb pain, but no such effect after EStim. These findings would suggest that the central desensitization effect of BreESTim could be translated to analgesic effects in patients with PLP. Furthermore, the findings of analgesic effects along with desensitization effects in patients with PLP support central sensitization as a plausible mechanism that mediates post-traumatic PLP.

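### No outcome is named primary and no multiplicity rule is stated, although each experiment tests 9 to 18 variables; VAS is only implied as primary and competes with duration, reduction times hours and electrical pain threshold

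*Combined protocol and SAP*

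**What the plan says.** Section 6 (Data Collection and Analysis) gives the same rule for Experiments 1 and 2. Two-way repeated-measures ANOVAs with factors INTERVENTION and TIME "will be tested on dependent variables, including VAS, QST thresholds (tactile, electrical, and thermal), to determine statistical significance between two interventions". Then "Paired t-tests will be used to compare the duration of lasting hours between two interventions" (Experiment 1; Experiment 2 has a matching sentence), and "p value is set at 0.05".

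For Experiment 3, section 6 lists VAS, modified VAS, the QST parameters, GWB and CES-D. The factors are INTERVENTION and TREATMENT, and TREATMENT has three levels: pre, post and follow-up. That paragraph gives no significance level. The level appears in the power text of section 4.C: "we applied the t-test (ANOVA) for difference of VAS in 2 x 2 crossover design with a 0.05 two-sided significance level".

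The QST list is in section 4.D: "QST includes tactile sensation threshold (TST), electrical sensation threshold (EST), electrical pain threshold (EPT), and thermal thresholds". The thermal part has four components: "Thermal thresholds (warm sensation, cold sensation, heat pain, cold pain) will be examined using a Medoc PATHWAY system".

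The only explicit rank is in the Experiment 3 design text of section 4.D: "The secondary outcome measurement will be General Well-Being (GWB) Schedule Survey", together with CES-D. Nothing is called primary. The power text for Experiment 1 rests on VAS: "A two-way repeated measures ANOVA was used to determine whether any change in VAS score was due to the interaction" of INTERVENTION with TIME. Experiment 3 is also sized on VAS.

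**The concern.** VAS looks like the main outcome, but the plan never says so, and other statements compete with it. Section 4.D says, for Experiments 1 and 3, that the treatment effect is quantified as pain reduction multiplied by hours. Duration has its own test in Experiments 1 and 2. For Experiment 3, section 6 ties the hypothesis to VAS reduction with a parallel rise in EPT, without saying whether both must be significant.

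Experiment 2 shows what this means in practice. Aim 2 hypothesises that the larger number of stimuli reduces pain more, but then expects a similar degree of reduction that lasts longer. With no primary outcome, a difference in either VAS or duration could be reported as confirming dose-response.

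The background (section 3a) promises direct evidence of clinical effectiveness and a demonstration of superiority over EStim. If the deciding outcome can be chosen after the data are seen, the 5% level does not apply to that claim.

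**Working it through.** **The plan's own figure.** The documents state no familywise error rate. The figure that can be checked is the Experiment 3 sample size, which is for one VAS test at two-sided 0.05. With a difference of 3.0, an SD of differences of 4.8 and N = 24, the noncentrality is (3.0/4.8) × √24 = 3.06. On 22 degrees of freedom the power is 83.3%, and 24/(1 − 0.20) = 30. So the size reproduces for a single test at the stated difference of 3.0. (The means printed beside it, 4.0 and 2.0, differ by 2.0; that is a separate matter.)

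**Counting tests.** I count one test per variable in section 6. QST has tactile, electrical sensation and electrical pain thresholds (3) plus four thermal thresholds, so 7 per site. Section 4.D can be read as one site (residual limb) or two (with the contralateral limb).

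- Experiments 1 and 2: VAS + 7 QST + duration = 9; with two sites, 1 + 14 + 1 = 16.
- Experiment 3: VAS + modified VAS + 7 QST + GWB + CES-D = 11; with two sites, 18. Section 6 does not list duration here.
- HRV is an outcome in section 4.D but is absent from section 6, so it is not counted.
- Section 4.C mentions QST in four limbs. That would give 1 + 28 + 1 = 30 tests in Experiment 1, but it conflicts with section 4.D and is not used in the range.

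**Independent tests, all nulls true.** The chance of at least one false positive in either direction is 1 − 0.95^k:

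| k | Result |
|---|---|
| 9 | 37.0% |
| 11 | 43.1% |
| 16 | 56.0% |
| 18 | 60.3% |

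**Correlated tests.** The documents give no correlations, so these values are assumptions. I simulated k two-sided t-tests on normal differences with a common correlation, 20,000 runs, with n = 14 for k = 9 and 16, and n = 24 for k = 11 and 18:

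| k | 0.3 | 0.5 | 0.7 |
|---|---|---|---|
| 9 | 33% | 28% | 21% |
| 11 | 38% | 31% | 23% |
| 16 | 48% | 39% | 28% |
| 18 | 52% | 40% | 29% |

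**Only tests that bear on the hypothesis.** Three would be, for example, VAS, duration and EPT at one site in Experiment 1. Five would add reduction times hours and EPT at a second site. Under independence, 1 − 0.95^3 = 14% and 1 − 0.95^5 = 23%.

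**Favourable direction only.** If tests are two-sided (stated only for Experiment 3) and independent, a false positive in favour of BreESTim has probability 1 − 0.975^k: 20%, 24%, 33% and 37% for k = 9, 11, 16 and 18.

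**The case against.** A hierarchy can be inferred. VAS is the sizing variable in Experiments 1 and 3, GWB and CES-D are expressly secondary, and the hypotheses name a joint pattern of pain reduction and raised EPT. A reader might infer that every unlabelled variable is primary by default, so that a superiority claim could rest on any one test, even a tactile or thermal threshold. The documents do not support that. A chance result on such a threshold would not meet the stated hypothesis, and it would run against the plan's own account that BreESTim leaves those thresholds unchanged.

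The large percentages are also conditional. They need every null to be true and the tests to be independent, and they count both directions. Modified VAS is built from VAS reduction and duration, so independence cannot hold exactly.

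Nor is the language uniformly confirmatory. Section 4.D says Experiment 2 is meant to explore dose-response. The Experiment 3 text uses the word exploratory and says that an improvement in baseline pain would justify a clinical trial. That remark sits in a paragraph about keeping medication constant, however, and does not reclassify the superiority comparisons.

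All of this limits the size of the problem. It does not remove it: sizing on VAS is not a declaration that VAS is primary, and the competing definitions of pain relief remain.

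**Conclusion.** The point holds in a qualified form and should be corrected. The available text names no primary outcome and no multiplicity control, and the implied choice of VAS is contested within the plan itself. The independence figures must be kept apart by experiment. A reader might infer that each experiment runs a risk of 37% to 60%, but that range pools the low end of Experiments 1 and 2 with the high end of Experiment 3.

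Even the narrowest count under independence (14%) is nearly three times the nominal 5%, and the lowest figure under the assumed correlations (21%) is about four times. These are chances of at least one nominally significant result, not of a false confirmation of the joint VAS and EPT pattern.

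One stretch of section 4.C, between the Experiment 2 pilot data and the Experiment 3 power text, was not available to me, so the sizing basis for Experiment 2 is unchecked.

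**What to change.** Add one paragraph to section 6 that names a single primary test per experiment, at two-sided 0.05:

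- **Experiment 1:** the VAS INTERVENTION × TIME interaction.
- **Experiment 2:** duration of analgesic effect, where section 6 itself expects the dose effect to appear. Revisit this if the Experiment 2 sizing text rests on another outcome.
- **Experiment 3:** the VAS INTERVENTION × TREATMENT contrast from pre to post-intervention, with follow-up secondary. The contrast must be named because TREATMENT has three levels.

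Make EPT at one named site the key secondary in each experiment, tested only if the primary is significant. Report modified VAS, the other thresholds, HRV, GWB and CES-D with confidence intervals or Holm-adjusted p-values, without superiority claims.

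The primary claim in each experiment then carries a 5% error rate, and the gate keeps primary and EPT together at 5%. No extra patients are needed, because Experiments 1 and 3 were already sized on one VAS test. Bonferroni over all variables would instead require 0.05/9 = 0.0056 down to 0.05/18 = 0.0028 per test. The cost is that secondary outcomes lose unadjusted significance claims.
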